Our goal is to investigate the efficiency of the newly designed ventilation grip. Specifically, we test the hypothesis that using the ventilation grip improves average tidal volumes achieved compared to the standard 2VE technique , thereby establishing a more effective seal and reducing perceived fatigue after prolonged periods of providing 2VE in a manikin simulation setting

Figure 1. The Mask Ventilation Grip

5) Inclusion and Exclusion Criteria*

Participants will be recruited via email. Novices (participants without any significant MV experience in a clinical setting) will be primarily recruited via contacting various University of Miami Miller School of Medicine clerkship directors who frequently utilize the CPS to train medical students. Whereas experts (participants with 2 or more years of clinical experience providing MV) will be primarily recruited via email distributed throughout the Department of Anesthesiology at the University of Miami Hospital and consisted of senior residents and attending physicians.

We propose a simulation based repeated-measures (mixed) cohort study that will include medical students, less-expereinced resident physicians and anesthesia attending physicians/anesthesia senior resident physicians with at least 2 or more years of experience. The study will be performed at the Center for Patient Safety at the University of Miami Miller School of Medicine campus..

Inclusion criteria:

- Current medical students, PGY1 residents or residents from other specialities with no prior experience in hand mask ventilation techniques
- Anesthesiology residents and attendings with at least 2 or more years of clinical experience

Exclusion criteria:

- Refusal to participate in the study.
- Medical students with prior experience in hand mask ventilation techniques (i.e. experiences in previous careers such as nursing or EMT professions)
- Any physical inability to adequately perform ventilation

6) Procedures Involved*

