After IRB approval and written informed consents, participating individuals will be categorized to novice or expert groups depending on previously described criteria/years of clinical experience. From these groups, they will be randomized via blindly selecting pieces of paper marked MVG or 2VE. There will be two boxes, one for novices with 16 pieces of paper (8 marked MVG/8 marked 2VE), and one for experts with 16 pieces of paper (8 marked MVG/8 marked 2VE.) Whichever option is selected (MVG or 2VE), the participant will begin with this technique and then switch to the alternative.

ev,The participants will then be guided to the OR simulator where the SimMan Essential patient stimulator (Laerdal Medical Wappingers Falls, NY) (manikin) will be placed supine on aa hospital bed. After this, mask holding technique with MVG device and without (2VE) will be demonstrated by investigators, who will then reviewparticipants' subsequent techniques to ensure consistency throughout the experiment. The parameters for the anesthesia workstation/OR simulator will be checked and confirmed by one or more members of the research team for every participant before the baseline information of participants' demographics and level of experience is recorded. They will be instructed to maintain as tight a seal between the mask/manikin face as possible, that the "patient" only requires mask ventilation during the entire scenario, and that there is no need to perform

additional emergency maneuvers such as chest compressions. The ventilation mask will be connected to an air flow supply via the anesthesia machine ventilator.

Participants will then don their desired sized gloves and perform MVG or 2VE for 30 breaths (approximately 3 minutes) in accordance with the techniques demonstrated previously as an investigator in the room records tidal volumes achieved for each breath onto a data sheet and a separate camera in the OR simulator also simultaneously records the encounter. Tidal volumes will not be recorded until a proper seal is established so participants are aware of what a mask leak feels like. After providing mask ventilation with MVG or 2VE for 30 total breaths, participants are given a 5-minute rest period during which they were to complete the given NASA-TLX and SOFI instruments described above.

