mL/cm H₂O, and the right manikin lung resistance set to 100 cm H₂O/L/sec while the contralateral lung is set to 0 cm H₂O/L/sec. These parameters were designed to mimic the feeling of providing 2VE to difficult patients (obese patient, short neck, obstructive sleep apnea, etc...) while maintaining a tidal volume (TV) of approximately 500 mL \pm 5 mLs. The height of the SimMan Essential Patients Stimulator (manikin) will be adjusted for each participant so that the top edge of the table is flush with the participants' iliac crests. An investigator with a timer will stand approximately 6 feet away from the participants with clear view of the monitors and participants' hands and give out instructions accordingly.

..

Measurements

Baseline information including age, gender and years of experience will be recorded.

Primary outcome: **the difference in the average tidal volume achieved per breath** between the two techniques (MVG and 2VE) in the two groups (novice and expert) as recorded by the anesthesia ventilator over the two 30 breath mask ventilation periods.

Secondary outcomes: Hand fatigue and **difficulty perception**. All participants (both novice and expert groups) will be asked to rate the difficulty of each of the techniques (MVG and 2VE) and express their level of fatigue appreciated by filling out NASA-TLX and SOFI instruments after providing ventilation with each technique.

Exploratory outcome:

Hand fatigue and efficacy of MVG compared to 2VE in regards to participants' hand sizes/grip strength. All participants will have their hand span, palm circumference, and maximum grip force of their dominant hand recorded. This data will be analyzed alongside each participant's answers to the previously described NASA-TLX, SOFI instruments, and gross average tidal volume for each period of ventilation with both techniques.

7) Statistical Analysis

The required sample size for this study was calculated with an online power and sample size calculator for general linear multivariate models (GLIMMMPSE v2.1.0) The parameters used for this study is in JavaScript Object Notation (i.e., JSON) file, which can be uploaded into GLIMMMPSE website and reviewed (URL for GLIMMMPSE program)

A data collection sheet will be used and completed for each included subject. Descriptive statistics will be used for demographic characteristics.

T-paired test model will be used for comparison of the tidal volumes between two groups (MVG and 2VE groups)

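### Technique order is randomised 8/8 in each experience group, but the planned paired t-test has no order term, so any period shift is counted as random error and costs power

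*Combined protocol and SAP*

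**What the plan says.** Section 6 (Procedures Involved) has each participant draw a slip that fixes the starting technique: "Whichever option is selected (MVG or 2VE), the participant will begin with this technique and then switch to the alternative". The novice box is described as "one for novices with 16 pieces of paper (8 marked MVG/8 marked 2VE". The expert box has the same make-up: "one for experts with 16 pieces of paper (8 marked MVG/8 marked 2VE". Order is therefore a randomised factor, balanced within experience group. The two periods are separated by a 5-minute rest, which is also used for the questionnaires.

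Under Measurements in section 6, the primary outcome is the difference in average tidal volume "between the two techniques (MVG and 2VE) in the two groups (novice and expert". Section 7 (Statistical Analysis) names one test for it: "T-paired test model will be used for comparison of the tidal volumes between two groups". No order, period or sequence term appears anywhere. Section 5 calls the study repeated-measures (mixed) and section 8 calls it a cross-over, but both describe the design and neither specifies a model. The text does not say whether the paired test is run within each experience group or on all participants together.

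**The concern.** In a two-period crossover, anything that changes tidal volume between the first and second period, such as learning or tiring, affects the within-person difference in opposite directions in the two orders. A paired t-test that ignores order leaves this systematic spread in its standard error. Balanced randomisation protects the estimate from bias, but the precision is recovered only if the analysis uses order.

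A shift is plausible on the plan's own terms. Section 2 takes change in tidal volume across the two ventilation periods as its objective measure of fatigue. The shift also need not be the same in both groups: the inclusion criteria admit students and residents "with no prior experience in hand mask ventilation techniques" alongside "Anesthesiology residents and attendings with at least 2 or more years of clinical experience". At stake are the chance of detecting a true difference in tidal volume and the width of its confidence interval.

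**Working it through.** **Inputs from the documents.** There are 8 participants per order in each group, so 16 per group and 32 in total (section 6). The test is a paired t-test (section 7), with 15 df per group or 31 df pooled.

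**Inputs not in the text.** The period shift, the standard deviation, the technique effect, alpha and power are not given. Section 7 reports a sample-size calculation but leaves its inputs in an external file, so there is no stated power to reproduce. Assumed here: two-sided alpha 0.05; 80% power; normal differences with the same SD in every group-by-order cell; one technique effect for both groups; no dropout.

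**Notation.** D is a participant's mean MVG minus mean 2VE tidal volume, τ the technique effect, p the period-2 minus period-1 shift, and s the SD of D within group and order.

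**Step 1, bias.** D has mean τ − p in MVG-first and τ + p in 2VE-first participants. With 8 of each, the average is [8(τ − p) + 8(τ + p)]/16 = τ, so there is no bias.

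**Step 2, variance.** The variance that the paired test estimates has expectation s² + p²·n/(n − 1), instead of s².

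**Step 3, detectable effect with order adjustment (noncentral t).**
- Per group: τ = 0.753 s, noncentrality 0.753 × √16 = 3.01, 14 df, power 80.0%.
- Pooled, with order, group and order-by-group: τ = 0.513 s, noncentrality 0.513 × √32 = 2.90, 28 df, power 80.0%.
- For the same effects with p = 0, the paired test has 80.4% (15 df) and 80.3% (31 df).

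**Step 4, inflation when p = τ.**
- Per group: 1 + 0.753² × 16/15 = 1.605, so the SD is multiplied by 1.27.
- Pooled: 1 + 0.513² × 32/31 = 1.272, so the SD is multiplied by 1.13.

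**Step 5, power by simulation** (200,000 trials per setting, same p in both groups):

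| p as a multiple of τ | Paired t, per group | Paired t, pooled | Order-adjusted, either |
|---|---|---|---|
| 0.25 | 79.2% | 79.8% | 80% |
| 0.5 | 76.0% | 78.4% | 80% |
| 1 | 62.6% | 72.4% | 80% |
| 1.5 | 42.0% | 62.3% | 80% |
| 2 | 21.2% | 48.9% | 80% |

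Calibrating τ instead to 80% power for the paired test with no shift (0.749 s and 0.511 s) gives almost the same result at p = τ: 62% and 72%.

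**Step 6, false positives.** With p at the size of the detectable effect and no true technique effect, the paired test rejects in about 1.5% (per group) and 2.9% (pooled) of trials, against a nominal 5%. It is conservative.

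**Step 7, different shifts in the two groups, pooled analysis:**

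| Novice p, expert p | Paired t | Order + group | With order-by-group |
|---|---|---|---|
| 0.5 s, 0 | 76.7% | 78.2% | 80.0% |
| 1.0 s, 0 | 65.0% | 71.9% | 79.9% |
| 0.5 s, −0.5 s | 73.0% | 72.2% | 80.1% |

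A single common order term is not enough if the groups are pooled and their shifts differ.

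**Step 8, scale.** If s were 25, 50 or 100 mL (assumed), a shift equal to the detectable effect would be 0.753 s = 19, 38 or 75 mL per group, or 0.513 s = 13, 26 or 51 mL pooled. The set tidal volume is about 500 mL (section 6).

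**The case against.** The strongest reply is that nothing here is invalid. A paired t-test in an order-balanced crossover gives an unbiased estimate and a conservative test, so an order term improves efficiency but corrects no error. The loss also depends on a shift that the documents never quantify, and several features should keep it small. Both techniques are demonstrated and investigators check how they are performed. "Tidal volumes will not be recorded until a proper seal is established". Breaths are machine-delivered at a fixed rate and pressure, each period lasts about three minutes, and there is a 5-minute rest. Section 5 also describes novices more loosely in its recruitment text, as lacking significant clinical experience, so a difference in shift between the groups is conjecture. Finally, the pooled scenarios assume one technique effect for both groups, whereas the primary hypothesis expects a larger gain in novices.

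Much of this stands. Validity is not in question, and shifts up to half the detectable effect cost little. No passage suggests a shift of 1.5 or 2 times that effect; those rows only show the trend. The per-group figures are the closer match to the primary outcome as worded. But these features do not show that the shift is negligible, and neither the design labels nor the unseen sample-size file puts an order term into the stated analysis. The trade is also one-sided: the term costs at most 0.4 points if it proves unnecessary, and omitting it costs about 17 points per group, or 8 pooled, if the shift matches the effect.

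**Conclusion.** The concern holds as a matter of precision. The plan randomises order in balance and then does not use it in the analysis. With a period shift equal to the detectable technique effect, power falls from 80% to 63% within a group of 16, or to 72% with 32 pooled. With half that shift it is 76% or 78%, and with a quarter the loss is 1 point or less. The algebra is certain. The size of the loss in this trial is not, because it depends on p and s, which the documents do not give, and on the assumed alpha and power.

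The absence of bias also depends on equal numbers completing each order. With 8 MVG-first and 6 2VE-first completers, for example, the plain paired mean would be off by p × (6 − 8)/14 = −p/7. The order-adjusted estimate would not.

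**What to change.** In section 7, replace the plain paired test for tidal volume with the following.

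- **Within each experience group:** regress D (mean MVG minus mean 2VE tidal volume per participant) on order, effect-coded as MVG-first or 2VE-first. Report the intercept with its 95% CI as the technique effect (14 residual df with 16 participants).
- **If the groups are pooled:** fit effect-coded order, group and order-by-group (28 residual df with 32 participants). Without the interaction, full power is recovered only if novices and experts have the same period shift.
- **Limit to state:** the model removes an additive period shift and does not address differential carryover between techniques.

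The section should also say whether the primary analysis is by group or pooled.

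The cost is SAP wording only. No extra participants or data are needed, since order is known from the draw. With no period shift, the price is one df per group (14 against 15) and 80.0% against 80.4% power, or three df pooled (28 against 31) and 80.0% against 80.3%.
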